5.2.4. Analyses for Categorical Endpoints

The frequency and percentage for each category will be presented.

5.2.5. Analyses for Time-to-Event Endpoints

For a participant who experiences the event, the time to event will be the study day corresponding to the actual date of the event or the earliest visit date at which the participant has already experienced the event. For all participants who have not experienced the event, their time to event will be right censored at the last available measurement time (or visit) used to define whether the participant experienced the associated event.

Time-to-event endpoints will be summarized using the Kaplan-Meier method and estimated survival curves will be displayed graphically. Graphs will describe the number of patients at risk over time. The median and quartiles will be estimated by the Kaplan-Meier method. 95% CIs for the median and quartiles will also be provided.

The log-rank test (stratified using baseline disease severity) p-value will be used for comparing time to event data between treatment groups.

5.3. Methods to Manage Missing Data

5.3.1. Binary Endpoints

For binary endpoints analyzed at each scheduled timepoint separately, visit windows ([Appendix 2](#)) will be used to map all observed data into nominal visits. After mapping, missing data will be handled by one of the following methods.

Method 1: any observations missing intermittently (including baseline values) will be considered missing completely at random (MCAR) and will remain missing in the analysis. This method is based on Estimand 1 and Estimand 3.

Method 2: additional analyses will utilize the longitudinal nature of the binary endpoint. A Generalized Linear Mixed Model (GLMM) will be fit to all observed data (ie, regardless of rescue therapy and without defining missing data as “non-response”). The binary outcome will be modeled using a logistic-normal distribution. Fixed factors will include treatment (abrocitinib and dupilumab), visit (Weeks 2, 4, 8, 12, 16, 20, 26) and treatment-by-visit interaction. Visit will be modeled as a categorical covariate. A participant-specific random intercept will be used to model the correlation within a participant over time ([Appendix 3](#)). Missing observations will be multiply imputed under the assumption that the missing data mechanism is MAR. Using the estimated posterior predictive distribution of the GLMM model parameters obtained using Markov Chain Monte Carlo (MCMC) methods, estimates of the posterior predictive probability of response will be calculated for each treatment group. A single imputation of the missing value will be sampled from a Bernoulli distribution with the corresponding posterior predictive probability of response. This imputation will be repeated multiple times with different MCMC samples to obtain multiple completed datasets. For each such completed dataset, the estimates of the proportions and CMH-weighted difference of proportions between abrocitinib and dupilumab will be obtained along with the associated standard errors using the methods in [Section 5.2.1](#). Rubin’s rule (Rubin, 1987) will be used to combine the multiple estimates and standard errors across the imputed datasets and provide p-values. More detailed descriptions are provided in [Appendix 3](#).

Method 2 is based on Estimand 4 treatment policy estimand and will be used for the supplementary analysis of the primary and key secondary endpoints.

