6.3. Measures to Minimize Bias: Randomization and Blinding

6.3.1. Allocation to Study Intervention

Allocation of participants to treatment groups will proceed through the use of an IRT system (interactive Web-based response [IWR]). The block randomization method will be used, and participants will be stratified by baseline disease severity (IGA = 3 vs. IGA = 4). The site personnel (study coordinator or specified designee) will be required to enter or select information including but not limited to the user's identification (ID) and password, the protocol number, and the participant number. The site personnel will then be provided with a treatment assignment, randomization number, and dispensable unit (DU) or container number when study intervention is being supplied via the IRT system. The IRT system will provide a confirmation report containing the participant number, randomization number, and DU or container number assigned. The confirmation report must be stored in the site's files.

Study intervention will be dispensed at the study visits summarized in the [SoA](#).

Returned study intervention must not be re-dispensed to the participants.

The study-specific IRT reference manual and IP manual will provide the contact information and further details on the use of the IRT system.

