5.2.1. Analyses for Binary Endpoints

Binary data at each scheduled visit will be analyzed by two approaches: (1) the test of hypothesis (and the p-value) of no difference between two treatment groups will be conducted by the Cochran-Mantel-Haenszel (CMH) statistic adjusting for baseline disease severity (IGA moderate or severe); p-values from the CMH statistic will be used to test the hypothesis of no difference in binary responses between two treatment groups; and (2) the proportion of responders in each treatment group will be reported and differences between two treatment groups will be summarized by the weighted difference and its 95% confidence interval obtained by normal approximation. Specifically, for NI of EASI-90 at Week 16 between abrocitinib and dupilumab, the 95% CMH weighted confidence interval will be constructed for the response difference and NI will be declared if the lower bound of the confidence interval is greater than -10%. The difference in proportions will be calculated within each randomization stratum. The final estimate of the difference in proportions will be a weighted average of these stratum-specific estimates using CMH weights. The CMH weight w_k for stratum k ($k = 1, 2$) is given by,

$$w_k = \frac{\frac{n_{ik} n_{ck}}{n_{ik} + n_{ck}}}{\sum_{j=1}^2 \frac{n_{ij} n_{cj}}{n_{ij} + n_{cj}}}$$

where n refers to sample size, the subscript c refers to the dupilumab group and the subscript i refers the abrocitinib group. The difference is estimated as $\hat{d} = \sum_{k=1}^2 w_k (\hat{p}_{ik} - \hat{p}_{ck})$, where \hat{p} refers to the estimated proportion. An estimate for \hat{p} is obtained as x/n , where x is the number of responders.

Two-sided 95% confidence intervals for the difference (based on a normal approximation) are formed by:

$$\hat{d} \pm 1.96 \sqrt{\sum_{k=1}^2 w_k^2 \left(\frac{\hat{p}_{ik}(1 - \hat{p}_{ik})}{n_{ik}} + \frac{\hat{p}_{ck}(1 - \hat{p}_{ck})}{n_{ck}} \right)}$$

In the above formula, the standard error is $\sqrt{\sum_{k=1}^2 w_k^2 \left(\frac{\hat{p}_{ik}(1 - \hat{p}_{ik})}{n_{ik}} + \frac{\hat{p}_{ck}(1 - \hat{p}_{ck})}{n_{ck}} \right)}$. When the number of responders is zero ($x = 0$), then \hat{p} will be replaced by $0.5/(n + 1)$. This change will be made only for calculating the standard error of \hat{d} and not anywhere else.

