6.4. Subset Analyses

Summary statistics for the primary and key secondary endpoints will be presented by subgroups below.

- Age (years) group (<40, ≥40; <65, ≥65);
- Sex (Male, Female);
- Race (White, Black or African-American, Asian, Other);¹
- Region of enrollment (US/Canada/Australia, Europe, Asia);
- Weight (kg) (<70, 70 to 100, >100 kg);
- AD Duration (years) group (<26, ≥26);
- Baseline disease severity (moderate, severe);
- Baseline EASI group (16-25, >25);
- Baseline % BSA group (10-30, >30-50, >50);
- Previous cyclosporine exposure (cyclosporine naïve, cyclosporine exposed);
- Prior AD medications (topical agents only, systemic agents)

Estimates of the response of and difference between abrocitinib and dupilumab, along with the 95% confidence interval (no p-value), will be presented for each defined category of each subgroup. For the binary endpoints, analyses will be performed using normal approximation without any adjustments for baseline disease severity.

The primary purpose of the subgroup analyses is to check for consistency and robustness of results across subgroups, to make sure overall results are not being driven by some subset of participants.

Graphical display (eg, forest plots) of the differences between treatment groups will be presented. There is no intention to have any specific inference within subgroups.

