Appendix 3. A Logistic-Normal GLMM for Longitudinal Binary Data and Multiple Imputations

Let Y_{ij} be the binary outcome for participant i ($i = 1, 2, \dots, N$) and post baseline visit j ($j = 1, \dots, 7$) for Weeks 2, 4, 8, 12, 16, 20 and 26. We assume $Y_{ij} = 1$ for a response and $Y_{ij} = 0$ for a non-response. Then we model as

$$P(Y_{ij} = 1 | x_{ij}, u_i) = \frac{e^{\beta' x_{ij} + u_i}}{1 + e^{\beta' x_{ij} + u_i}} \equiv \pi_{ij}(\beta; u_i)$$

Here, β is a vector of unknown parameters corresponding to the vector of fixed effects x_{ij} and u_i is a participant-specific random effect which is assumed to be normally distributed with mean 0 and variance σ^2 . Note that conditional on u_i , Y_{ij} is independent of Y_{ik} , when $j \neq k$.

The full marginal likelihood of the data is then,

$$L(\beta, \sigma^2) = \prod_{i=1}^N \int_{-\infty}^{\infty} \prod_{j=1}^7 \pi_{ij}(\beta; u_i)^{Y_{ij}} (1 - \pi_{ij}(\beta; u_i))^{(1-Y_{ij})} \times N(u_i; 0, \sigma^2) du_i$$

There is no closed analytical form for this likelihood.

For the present study, the primary and key secondary endpoints are evaluated at Week 2, 4 and 16 ($j = 1, 2$) and 5. There are 2 treatment groups, so the model term $\beta' x_{ij}$ when written out looks like,

$$\beta_0 + \sum_{k=1}^2 \beta_{1k} \times 1_{(T_i=k)} + \beta_{2j} + \sum_{k=1}^2 \beta_{3jk} \times 1_{(T_i=k)}$$

Here, T_i represents treatment for participant i where $T_i = 1$ if the participant is randomized to abrocitinib, and $T_i = 2$ if the participant is randomized to dupilumab. The third term β_{2j} in the expression is the effect for visit j and the fourth term in the expression is the interaction effect between treatment and visit. With an overall intercept term, the model is over-parameterized as written and so to fit the model, some restrictions on β are required. The default option in many standard statistical software is to assume $\beta_{12} = 0, \beta_{27} = 0$, thereby interpreting β_{11} as the difference in treatment effect relative to $T = 2$ and β_{2j} as the difference in visit effect relative to $V = 7$. Consequently, $\beta_{3jk} = 0$ when $j = 7$ or $k = 2$. So, for example, for a participant taking abrocitinib at Week 16, the expression would be $\beta_0 + \beta_{11} + \beta_{25} + \beta_{351}$. For a participant taking dupilumab at Week 4, the expression would be $\beta_0 + \beta_{22}$.

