The saturated logit-normal GLMM as described above will be used as the imputation model. Estimation of the model parameters will be performed under the Bayesian framework using Markov Chain Monte Carlo (MCMC) methods. We assign a non-informative prior for each component of β to be independent and identically distributed as $\sim N(0, 10000)$ and assign a weakly informative prior for σ^2 as an Inverse-Gamma distribution with shape=1 and scale=1. With this prior distribution, the 90th percentile for σ^2 is approximately 9.

Let $\beta^b, u_i^b, b = 1, 2, \dots, B$ be a sample from the posterior distribution. A single imputation $\widetilde{Y}_{i,j}^b$ of missing Y_{ij} is based on the posterior predictive distribution of the response probabilities estimated from the GLMM. For example, if participant i is randomized to abrocitinib ($T_i = 1$), then at Week 16 ($V = 5$),

$$\text{logit}(\pi_{i,1,5}^b) = \text{logit}\left(P\left(\widetilde{Y}_{i,5}^b = 1 \mid T_i = 1, V = 5\right)\right) = \beta_0^b + \beta_{11}^b + \beta_{25}^b + \beta_{351}^b + u_i^b.$$

If participant i is randomized to dupilumab ($T_i = 2$), then at Week 16 ($V = 5$),

$$\text{logit}(\pi_{i,2,5}^b) = \text{logit}\left(P\left(\widetilde{Y}_{i,4}^b = 1 \mid T_i = 2, V = 5\right)\right) = \beta_0^b + \beta_{25}^b + u_i^b.$$

We then sample the single imputed value $\widetilde{Y}_{i,j}^b$ from a Bernoulli distribution with probability of success $\pi_{i,T_i,5}^b$.

Analysis of an imputed data set will produce an estimate as well as standard error of the treatment difference using CMH and normal approximation ([Section 5.2.1](#)). This is repeated for B (typically, $B=500$) times to generate B complete imputed data sets and these B sets of estimates are combined using the Rubin's Method (Rubin, 1987).

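### The imputation model for the binary endpoints omits baseline severity, the factor that stratifies both randomisation and the analysis of each imputed dataset

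*SAP*

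**What the plan says.** **Imputation model.** SAP 5.3.1, Method 2, states: "Fixed factors will include treatment (abrocitinib and dupilumab), visit (Weeks 2, 4, 8, 12, 16, 20, 26) and treatment-by-visit interaction". A participant-specific random intercept carries the within-participant correlation, and missing responses are imputed under MAR. SAP Appendix 3 writes out the linear predictor as intercept, treatment, visit and a final term, of which it says: "the fourth term in the expression is the interaction effect between treatment and visit". It then states: "The saturated logit-normal GLMM as described above will be used as the imputation model". Saturated here means saturated in treatment by visit; severity appears nowhere. Protocol 9.4.1 names the GLMM without listing covariates, so it does not supply the term either.

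**Analysis of the imputed data.** Appendix 3: "Analysis of an imputed data set will produce an estimate as well as standard error of the treatment difference using CMH and normal approximation". The method is that of SAP 5.2.1, where "The difference in proportions will be calculated within each randomization stratum" and the stratum results are combined with CMH weights. The strata come from Protocol 6.3.1: "participants will be stratified by baseline disease severity (IGA = 3 vs. IGA = 4".

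**Other models in the SAP.** The ANCOVA (5.2.2), the MMRM (5.2.3) and the log-rank test (5.2.5) all use baseline severity. Where the SAP leaves it out on purpose, it says so: for the asthma questionnaire MMRM (Appendix 8.2.5) and for the subgroup estimates (6.4). There is no such statement for the GLMM.

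**The concern.** An imputation model should contain at least the variables that the analysis model uses. Here stratum-specific response rates are computed from values imputed without knowledge of the stratum. If severity is related both to response and to missingness, imputed values for severe participants are pulled towards the arm average. The random intercept recovers part of the severity information through a participant's own observed responses. It recovers least for those who leave early.

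What is at stake is the value of the imputation as a check on the missing-data rule. At Weeks 2 and 4 it is the only planned supplementary analysis that changes that rule. Supplementary Analysis 1 stays with Method 1, of which SAP 5.3.1 says "This method is based on Estimand 1 and Estimand 3", and Supplementary Analysis 3 applies the main rule to a subset. At Week 16 the imputation stands beside a per-protocol analysis that requires an observed Week 16 EASI, and beside the Estimand 3 analysis.

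**Working it through.** The plan states no figure for this point, so the check is of size: how far would the imputed difference move?

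**Inputs from the documents.** 300 per arm. EASI-90 at Week 4: 12% on dupilumab and 12 + 15 = 27% on abrocitinib. EASI-90 at Week 16: 53% v 43%. Seven visits, logistic-normal model with a random intercept.

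**Assumed, because the documents give no values.** 40% severe; random-intercept SD 2; a severity log-odds as listed below; EASI-90 at Weeks 2, 8, 12, 20 and 26 of 12, 42, 49, 54, 55% (abrocitinib) and 4, 27, 37, 46, 48% (dupilumab). Drop-out depends only on arm and severity, is spread evenly before Weeks 2, 4, 8, 12 and 16, and leaves no later EASI.

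**Method.** A large-sample calculation without simulation noise. All response patterns are enumerated by arm and stratum, and the GLMM is fitted by maximising the expected likelihood (40-point quadrature, standing in for MCMC). Each missing response is replaced by its predictive probability given the participant's observed responses. Bias is the CMH-weighted difference after imputation minus the full-data value.

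**Standard errors for scale.**
- Week 16: √(0.53×0.47/300 + 0.43×0.57/300) = 4.06 points.
- Week 4: √(0.27×0.73/300 + 0.12×0.88/300) = 3.18 points.

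**Planned model, severity effect alike in both arms. Bias in points:**

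| Drop-out | Visit | log-odds −0.75 | −1.5 | −2.5 |
|---|---|---|---|---|
| Mild: 10% severe abrocitinib, 5% elsewhere | Week 16 | +0.09 | +0.18 | +0.30 |
| Extreme: 25% severe abrocitinib, 5% elsewhere | Week 16 | +0.39 | +0.77 | +1.25 |
| Extreme: 25% severe dupilumab, 5% elsewhere | Week 16 | −0.43 | −0.85 | −1.36 |
| 25% severe, 5% moderate, both arms | Week 16 | −0.04 | −0.08 | −0.12 |
| Extreme: 25% severe abrocitinib, 5% elsewhere | Week 4 | +0.16 | +0.31 | +0.48 |
| Extreme: 25% severe dupilumab, 5% elsewhere | Week 4 | −0.10 | −0.18 | −0.27 |

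Stratum rates move more than the overall difference. With log-odds −1.5 and 25% drop-out among severe abrocitinib participants, the Week 16 rate in that cell is 41.9% after imputation against 39.6% in full data.

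**Which terms to add.** With equal severity effects, a main effect alone brings the bias to 0.00. With effects that differ by arm (−0.75 abrocitinib, −2.25 dupilumab), Week 16 bias is:

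| Drop-out | No term | Main effect | Plus treatment-by-severity |
|---|---|---|---|
| 25% severe abrocitinib, 5% elsewhere | +0.36 | −0.39 | 0.00 |
| 25% severe dupilumab, 5% elsewhere | −1.28 | −0.46 | 0.00 |
| 25% severe, 5% moderate, both arms | −0.91 | −0.81 | 0.00 |

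The zeros arise because the fitted model then matches the assumed data.

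**Severity effect changing over visits** (Week 16 bias, no term → both terms):
- growing from −0.5 to −2.5 in both arms, 25% severe abrocitinib drop-out: +1.20 → +0.41;
- shrinking from −2.5 to −0.5 in both arms, same drop-out: +0.37 → −0.36;
- growing in abrocitinib and shrinking in dupilumab, 25%/5% drop-out in both arms: +0.68 → +0.59.

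**EASI after drop-out.** The protocol's Schedule of Activities collects EASI at EOT/ED and four weeks later. Protocol 7.3 keeps participants who stop treatment in the study for both visits. SAP Appendix 2 assigns visits by study day. For Week 16 (Days 100–127), an EOT visit on those days counts directly; one on Days 72–99 has its follow-up on Days 72 + 28 = 100 to 99 + 28 = 127. For Week 4 (Days 23–43), an EOT visit on Days 2–15 has its follow-up on Days 30–43. Treating the last drop-out interval and half of the Week 12 interval as observed (a simplification), the Week 16 extreme abrocitinib row falls to +0.31, +0.62, +1.01 and the mild row to +0.07, +0.15, +0.24.

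**The case against.** The strongest case against is that this is immaterial and a matter of modelling taste. The imputation is supplementary (SAP 2.1.4, 5.3.1) and outside the testing sequence (5.1), and the random intercept already carries part of the severity information. Bias approaches 1 point or more only if drop-out depends strongly on arm and severity together, or if the severity effect differs by arm or over visits. The documents establish none of these. Scheduled EASI after stopping treatment would shrink the figures further, and the proposed terms do not help in every scenario.

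Most of this stands, and it limits the size of the point. The post-drop-out argument has two conditions. Participants who withdraw completely supply no follow-up. And SAP 4 censors data after drop-out unless otherwise specified, so the statements in 5.3.1 and Appendix 1 that all observed data enter the imputation must be read as the exception.

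It does not follow that the omission is mere preference. Which interactions to include is a judgement; leaving the randomisation stratum out of a model whose output is analysed by that stratum is a mismatch, and the SAP gives no reason for it.

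A reader might infer that the primary or key secondary conclusions are biased. The documents do not support that: the main Estimand 1 analyses are stratified by severity and do not use this model. A reader might also infer that the two added terms cure the bias. The calculations with a changing severity effect show otherwise.

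**Conclusion.** The mismatch is real and minor. Baseline severity is absent from the imputation GLMM in both places where it is specified, while randomisation, the CMH analysis of the completed data and the SAP's other models use it. MAR is therefore not conditional on a stratum the trial already holds.

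Under the assumptions listed, with a severity effect alike in both arms, the Week 16 bias is 0.1 to 0.3 points in the mild case and at most about 1.3 to 1.4 points in the extreme one. That is at most about a third of the standard error (1.36/4.06 = 0.33). These are upper bounds for their scenarios, provided the imputation uses EOT/ED and follow-up EASI. At Week 2 the effect is negligible, because a daily diary value anywhere in Days 2–22 fills the window. The severity effect, severe share, drop-out and random-intercept SD are all assumptions, so the figures show scale and do not predict this trial's result. No formal claim depends on the analysis.

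**What to change.** Add baseline disease severity (moderate/severe) and a treatment-by-severity term to the GLMM fixed effects in SAP 5.3.1, Method 2, and to the linear predictor in Appendix 3. The purpose is to align the imputation with the stratified analysis. The interaction is worth including because a main effect alone leaves bias of similar size in some cases where the severity effect differs by arm, and SAP 6.4 already plans to examine the treatment difference by severity.

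The cost is two model parameters, with no new data and no new table. Protocol 9.4.1 lists no GLMM covariates, so the protocol-specified analysis is unchanged, and no other analysis needs to change.

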5.3.2. Continuous Endpoints

In general, all observations after dropout or use of rescue therapy will be censored first. For non-PRO (patient reported outcome) continuous endpoints measured longitudinally, missing values post-baseline will not be imputed explicitly. For such endpoints, assuming that the missing data mechanism is missing at random (MAR), the data will be analyzed based on a restricted maximum likelihood (REML) using a linear mixed-effect model with repeated measures for these continuous variables ([Section 5.2.3](#)). This model will yield valid inferences in the presence of a missing data mechanism that is MAR. This method is based on Estimand 2 hypothetical estimand.

For the continuous PRO variables such as DLQI, POEM, HADS, and EQ-5D-5L, rules suggested by the developers of these instruments will be followed in calculating the missing

values. If these rules are not enough for imputing a value, then the missing values will be handled in the same way as non-PRO variables.

6. ANALYSES AND SUMMARIES

A summary of analyses for clinical efficacy endpoints is provided in [Appendix 1](#). Visit windows to be used for all efficacy analyses and some relevant safety analyses are detailed in [Appendix 2](#).

6.1. Primary Endpoint(s)

6.1.1. Week 2 PP-NRS4 Response

6.1.1.1. Main Analysis

- Estimand strategy: Estimand 1, composite estimand ([Section 2.1.1](#)).
- Analysis set: FAS ([Section 4](#)). Participants must have baseline PP-NRS ≥ 4 to be included.
- Analysis methodology: CMH and normal approximation in [Section 5.2.1](#).
- Intercurrent events and missing data: The intercurrent event is captured through the variable definition; for participants who drop out for any reason or use rescue therapy, the response will be defined as “non-responsive” after that point.
- The number of participants, number and percent of response at Week 2 along with the 95% confidence interval by normal approximation will be presented for each treatment arm.
- The CMH test p-value, the estimate of the difference in proportions of response at Week 2 along with the 95% confidence interval by CMH normal approximation will be presented for abrocitinib versus dupilumab.

